2.5.3 Handling of missing values/censoring/discontinuations

Missing data for the primary endpoint will be imputed using a multiple imputation approach that assumes that the missingness mechanism can be retrieved from observed data (missing at random; MAR). The imputation model will be fitted within each treatment and stratum, using MCMC method, based on the longitudinal sequence of body weight data collected at each visit up to and including Week 12. .

2.5.4 Supportive analyses

As a sensitivity analysis, the dose-response modeling as described in [Section 2.5.2](#) will be conducted in the PPS as well. In addition, the same dose-response modeling will be conducted in the FAS using on-treatment weight data only. On-treatment data refer to those collected during the double-blind period, and prior to or within 7 days of the final study medication intake date.

Summary statistics for body weight will be presented by visit by treatment for observed and imputed values. The summary statistics n, mean, SD, median, minimum, maximum, Q1 and Q3 will be presented for the BL values and similarly for absolute values at and percent changes from BL to the post-BL visits. Also summary statistics will be presented using observed values only by visit, treatment, and subgroup of interest: baseline glycemic status, age group, gender, and BMI category.

Figures will be produced to visually show the raw and the imputed mean percent changes by visit over 12 weeks of Epoch 3 for each treatment group, for all subjects and by strata separately.

2.6 Analysis of the key secondary objective

There is no key secondary objective for the study.

2.7 Analysis of secondary efficacy objective(s)

2.7.1 Secondary endpoints

- Responder rates based on percent decrease in body weight from BL at Week 12 $\geq 3\%$, $\geq 5\%$, or $\geq 10\%$
- Dose-response relationship in dysglycemic subjects and subjects with T2DM after 12 weeks of treatment.
- Change from BL at Week 12 in waist circumference at umbilical level.
- Change from BL at Week 12 in HbA1c
- Change from BL at Week 12 in FPG
- Change from BL at Week 12 in SBP and DBP
- Percent changes from BL at Week 12 in the fasting lipid profile (TG, total cholesterol, HDL cholesterol, LDL cholesterol, lipoproteins, calculated VLDL cholesterol and non-HDL cholesterol)
- Change from BL at Week 12 in \log_{10} -transformed hsCRP
- Change from BL at Week 12 in uric acid
- Change from BL at Week 12 in urine albumin
- Change from BL at Week 12 in urine albumin to creatinine ratio
- Change from BL at Week 12 in fat area parameters (VFA and SFA)

2.7.2 Statistical hypothesis, model, and method of analysis

Analysis method: responder analysis

For the responder analysis, a logistic regression model will be performed using the percent decrease in body weight from BL at Week 12 $\geq 3\%$, $\geq 5\%$ or $\geq 10\%$ (yes/no) as a response variable, treatment, and glycemic stratification factor as fixed factors and BL body weight as a covariate, respectively. The Week 12 missing values will be imputed using the multiple imputation method as described in [Section 2.5.3](#). In order to account for the imputation uncertainty, this logistic regression model will be repeated for each imputed dataset, which results in a set of estimated odds ratio and its 95% confidence interval of an LIK066 dose vs placebo for all dose groups. Rubin's rule will be used to combine the multiple sets of odds ratios and 95% confidence intervals to a single set of odds ratio and its 95% confidence interval of an

LIK066 dose *vs* placebo. Similar analysis by glycemic status stratification factor will be performed to assess the responder across each of the subgroups (subjects with dysglycemic and subjects with T2DM).

In addition, subjects meeting the pre-defined response criteria (percent decrease in body weight from BL at Week 12 $\geq 3\%$, $\geq 5\%$ or $\geq 10\%$) will be summarized by treatment for all subjects and by glycemic stratification factor. Cochran-Mantel-Haenszel-test will be performed to compare each dose to the placebo using observed values.

Analysis method: dose-response relationship by glycemic stratification factor

For the dose-response relationship in subjects with dysglycemic and subjects with T2DM, the dose-response modeling with the same candidate model sets for the primary variable as described in [Section 2.5.2](#) will be performed on percent change of body weight from BL at Week 12 for these two subsets of subjects separately.

Analysis for other secondary endpoints

Other efficacy secondary endpoints are analyzed using ANCOVA models.

- For changes from BL at Week 12 in HbA1c, FPG, lipid parameters, fat area parameters, uric acid, urine albumin, urine albumin to creatinine ratio, and log10-transformed hsCRP, an ANCOVA model will be applied for individual variables, including treatment and baseline glycemic status as fixed effect factors, and baseline as a covariate.
- For changes from BL at Week 12 in other variables, a repeated measure ANCOVA model will be applied with treatment, visit, baseline glycemic status, and treatment by visit interaction as fixed-effect factors and baseline as a covariate, and an unstructured covariance matrix among visits common between treatments.

The adjusted mean changes at Week 12 within each treatment, the differences in mean changes at Week 12 between the LIK066 and placebo treatments, and their 95% confidence intervals obtained from the above model will be presented.

In addition, ANCOVA analyses will be applied by baseline glycemic status.

- For changes from BL at Week 12 in HbA1c, FPG, lipid parameters, fat area parameters, urine albumin, urine albumin to creatinine ratio, and log10-transformed hsCRP, an ANCOVA model will be applied for individual variables, including treatment as a fixed effect factor, and baseline as a covariate.
- For changes from BL at Week 12 in other variables, a repeated measure ANCOVA model will be applied with treatment, visit, and treatment by visit interaction as fixed-effect factors and baseline as a covariate, and an unstructured covariance matrix among visits common between treatments.

The adjusted mean changes at Week 12 within each treatment, the differences in mean changes at Week 12 between the LIK066 and placebo treatments for each stratum, and their 95% confidence intervals obtained from the above models will be presented by strata for each efficacy endpoint.

Summaries of absolute values and change from BL by treatment group and visit will be presented for all secondary efficacy variables for all subjects and by strata. Figures will be produced to visually show the raw mean changes by visit over 12 weeks of Epoch 3 for each treatment group, for overall and by strata separately.

All analyses on secondary variables will be performed in the FAS.

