5.2 Treatment arms

All subjects entering Epoch 2 (run-in) will receive placebo.

At Visit 201 (randomization), subjects eligible for randomization will be assigned 2:2:3:3:3 to one of the following treatment arms in Epoch 3 (see [Section 3.1.2](#)):

- 2.5 mg qd LIK066 (approx. 20 subjects)
- 10 mg qd LIK066 (approx. 20 subjects)
- 25 mg qd LIK066 (approx. 30 subjects)
- 50 mg qd LIK066 (approx. 30 subjects)
- Placebo (approx. 30 subjects)

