9.5 Analysis of secondary variables

9.5.1 Efficacy variables

Variables

- Responder rates based on percent decrease in body weight from BL at Week 12 $\geq 3\%$, $\geq 5\%$, or $\geq 10\%$
- Dose-response relationship in dysglycemic subjects and subjects with T2DM after 12 weeks of treatment.
- Change from BL at Week 12 in waist circumference at umbilical level.
- Change from BL at Week 12 in HbA1c

- Change from BL at Week 12 in FPG
- Change from BL at Week 12 in SBP and DBP
- Changes from BL at Week 12 in the fasting lipid profile (TG, total cholesterol, HDL cholesterol, LDL cholesterol, lipoproteins, calculated VLDL cholesterol and non-HDL cholesterol) and hsCRP
- Change from BL at Week 12 in uric acid
- Change from BL at Week 12 in urine albumin
- Change from BL at Week 12 in urine albumin to creatinine ratio
- Change from BL at Week 12 in fat area parameters (VFA and SFA)

Analysis method: responder analysis

For the responder analysis, a logistic regression model will be performed using the percent decrease in body weight from BL at Week 12 $\geq 3\%$, $\geq 5\%$ or $\geq 10\%$ (yes/no) as a response variable, treatment, and glycemic stratification factor as fixed factors and BL body weight as a covariate, respectively. The Week 12 missing values will be imputed using the multiple imputation method as described in [Section 9.4.3](#). In order to account for the imputation uncertainty, this logistic regression model will be repeated for each imputed dataset, which results in a set of estimated odds ratio and its 95% confidence interval of an LIK066 dose vs placebo for all dose groups. Rubin's rule will be used to combine the multiple sets of odds ratios and 95% confidence intervals to a single set of odds ratio and its 95% confidence interval of an LIK066 dose vs placebo. Similar analysis by glycemic status stratification factor will be performed to assess the responder across each of the subgroups (subjects with dysglycemic and subjects with T2DM).

In addition, subjects meeting the pre-defined response criteria (percent decrease in body weight from BL at Week 12 $\geq 3\%$, $\geq 5\%$ or $\geq 10\%$) will be summarized by treatment for all subjects and by glycemic stratification factor. A Cochran-Mantel-Haenszel-test will be performed to compare each dose to the placebo.

Analysis method: dose-response relationship by glycemic stratification factor

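### Placebo may well have no patient with ≥10% weight loss; the planned odds ratios, and sometimes the CMH test, then cannot be estimated, and the SAP has no rule for it (minor)

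*SAP*

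**What the plan says.** SAP 2.7.2 states that "a logistic regression model will be performed using the percent decrease in body weight from BL at Week 12", dichotomised at ≥3%, ≥5% and ≥10%. Treatment and stratum are factors, baseline weight is a covariate, and each dose is compared with placebo. The model is fitted in every imputed dataset; in the words of Protocol 9.5.1, "Rubin's rule will be used to combine the multiple sets of odds ratios and 95% confidence intervals to a single set of odds ratio". It is then repeated within strata: "Similar analysis by glycemic status stratification factor will be performed to assess the responder across each of the subgroups". On imputation, SAP 2.5.3 says: "The imputation model will be fitted within each treatment and stratum". As a further analysis, "Cochran-Mantel-Haenszel-test will be performed to compare each dose to the placebo using observed values", alongside responder summaries by treatment and stratum.

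Neither document names a penalised or exact method, a minimum number of events, or a rule for imputed datasets in which the fit diverges. SAP 2.1 has a feasibility proviso, but it concerns the stratification factor in ANCOVA models. SAP 2.6 limits the weight of the issue: "There is no key secondary objective for the study".

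**The concern.** Placebo is the common reference. If it has no ≥10% responder, maximum likelihood has no finite solution for any of the four odds ratios. The ratio is infinite for a dose arm with a responder and undefined for one without. Because imputation is done within arm and stratum, the other arms do not help to fill an empty placebo cell.

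The ≥10% rate is a stated secondary endpoint, overall and by subgroup, and the pooled odds ratio is its only effect estimate that uses the imputed data. Without a rule, the fallback would be chosen after the data are seen.

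**Working it through.** **Inputs.** From the documents: arms of 30/20/20/30/30 for placebo and 2.5, 10, 25 and 50 mg (Protocol 5.2); each stratum to hold at least 45% of patients (Protocol 5.3), so about 13-15 of the 30 placebo patients, taken here as 15; SD 3 or 3.5% and best-dose effect 3.5 or 4.0% (SAP 3); 10% loss of information (SAP 3), so 27 of 30 or 18 of 20. Assumed: a placebo mean μ of 0 to -3% from the post-run-in baseline, with -4% and -5% as stress cases, and a normal percent change.

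**The plan's own figure.** With effective arms of 27/18/18/27/27, the six candidate shapes and a one-sided 2.5% multivariate-t critical value of 2.257, average power comes to 99.69/98.12/99.97/99.59% and minimum power to 99.51/97.30/99.94/99.37%. All are within 0.03 points of the SAP table, so the inputs are read correctly.

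**Empty placebo cell at ≥10%.** p = Φ((-10 - μ)/SD) and P(none) = (1 - p)^n. Example, μ = -2, SD 3.5: p = Φ(-2.286) = 0.01114; 0.98886^30 = 0.715; 0.98886^15 = 0.845.

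| μ | n=30, SD 3 / 3.5 | n=15, SD 3 / 3.5 |
|---|---|---|
| 0 | 0.987 / 0.938 | 0.994 / 0.968 |
| -1% | 0.960 / 0.859 | 0.980 / 0.927 |
| -2% | 0.891 / 0.715 | 0.944 / 0.845 |
| -3% | 0.744 / 0.501 | 0.862 / 0.708 |
| -4% (stress) | 0.501 / 0.266 | 0.708 / 0.515 |
| -5% (stress) | 0.230 / 0.092 | 0.480 / 0.303 |

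**What the fit does.** In a constructed dataset with 0/30 placebo responders, the planned model gave a 50 mg log odds ratio of 9.4 after 10 iterations and 24.4 after 25; its standard error went from 35 to about 64,000. The other three doses diverged with it.

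**Across imputations.** A simulation assumed 3 of 30 placebo Week 12 weights missing, correlation 0.8 with the earlier visit and 20 imputations (the SAP gives no number). At least one imputed dataset had an empty placebo cell in 54-99% of trials. In 10-29% some datasets were empty and others not, so a repair applied dataset by dataset would mix methods.

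**CMH test on observed values.** It has zero variance when both compared arms are empty, with probability (1 - p_placebo)^27 × (1 - p_dose)^m. Examples at μ = -2, SD 3.5, effect 4:
- 50 mg, m = 27: p_dose = Φ(-4/3.5) = 0.1265; 0.739 × 0.026 = 0.019.
- 2.5 mg, m = 18, Emax with ED50 5 mg: share of the 50 mg effect = (2.5/7.5)/(50/55) = 0.367, an effect of 1.47; p_dose = Φ(-6.53/3.5) = 0.031; 0.739 × 0.567 = 0.419.

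Over μ = 0 to -3% and both SDs and effects, the range is 0.2-66% for 50 mg and 19-96% for 2.5 mg.

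**Other thresholds within a stratum.** Taking 15/10/10/15/15 patients, the chance that some arm is empty or all responders is 1 - Π[1 - (1 - p)^n - p^n], before imputation. At ≥3% it is 2-49% (Emax, ED50 5 mg) or 3-28% (linear). At ≥5% it is 2-68% or 5-89%. An affected active arm spoils only its own odds ratio; an affected placebo arm spoils all four.

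**The case against.** - **The frequency is not a fact of the documents.** They give neither a placebo mean nor an expected ≥10% rate, and placebo patients receive diet and exercise advice at every visit. The normal tail also matters: with t tails on 5 degrees of freedom and the same SD, 50-99% becomes 47-89%. This stands. The supportable statement is conditional on a placebo mean of 0 to -3%, and a mean of 0 is its extreme end.
- **Pooling would not stop.** A reader might infer that one empty imputed dataset makes Rubin's rule impossible to apply. Ordinary software prints very large finite values, so pooling runs and returns an obviously useless interval. The failure is conspicuous and unlikely to mislead. That stands too, but the analysis as written still yields nothing usable.
- **The CMH test looks like a safe fallback.** It is only a partial one: it works when just one of the two compared arms is empty and is undefined when both are.
- **The remedy recovers little.** At ≥10% this is largely true, and one sentence declaring the ratio not estimable would close most of the gap. Firth fitting adds a defined estimate in the common case of responders on the dose but none on placebo.

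**Conclusion.** The point holds as a minor one. For ≥10% loss the documents prescribe an estimator that, under plausible placebo means, has no finite value in 50-99% of trials overall and 71-99% of strata, and they give no rule for that case. These figures rest on normality, the plan's SDs and an assumed placebo mean of 0 to -3%; overall they fall to 27-50% at -4% and 9-23% at -5%.

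A reader might go further and infer that the responder objective as a whole, or dose selection, is at risk. The documents do not support that. There is no key secondary objective, and Protocol 9.4.2 bases target dose selection on model-averaged mean weight loss. The primary test, the responder counts and the stratum analysis using "the dose-response modeling with the same candidate model sets for the primary variable" do not depend on this odds ratio. In the overall population the placebo cell at ≥3% is empty in at most 0.6% of trials.

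**What to change.** In SAP 2.7.2, before unblinding:

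1. For ≥10%, overall and by stratum, use Firth-penalised logistic regression in every imputed dataset. Pool log odds ratios and their standard errors by Rubin's rules, then back-transform.
2. For the by-stratum ≥3% and ≥5% analyses, pre-specify Firth outright. A switch triggered by an extreme arm would fire in 2-49% and 2-89% of strata, and one small arm would change the method for all doses.
3. Report both the odds ratio and the CMH test as not estimable when neither that dose arm nor placebo has an observed responder. This depends on observed data only, so it is the same in every imputation. Make the planned counts the main ≥10% summary.
4. List the change in SAP Section 4.

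The overall ≥3% and ≥5% fits can stay as planned. The residual risk of an empty placebo cell at ≥5% is 23% at a mean of 0 with SD 3, and below 1% at -2%.

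**Cost.** SAP wording and a fitting option. The estimates are shrunken and imprecise. Without covariates, 2/30 against 0/30 gives (2.5 × 30.5)/(28.5 × 0.5) = 5.35, with a Wald interval of 0.23-122. At a placebo mean of -2% and SD 3.5, the geometric mean Firth odds ratio for 50 mg is 4.7-6.2 against a true 9.8-12.9. Interval coverage is 94-96%, but the interval excludes 1 in only about 2-6% of trials. Rule 3 leaves the 50 mg cell blank in 0.2-66% of trials and the 2.5 mg cell in 19-96%, so low-dose cells will often be empty.

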2.7.3 Handling of missing values/censoring/discontinuations

Missing body weight at Week 12 will be imputed using the multiple imputation method as described in [Section 2.5.3](#).

Repeated measure ANCOVA models, which use all available data, will be used to analyze other secondary variables. The approach yields valid results, i.e. confidence intervals with correct coverage and tests with the correct size under a missing at random (MAR) process (Siddiqui et.al. 2009).

2.8 Safety analyses

All safety analyses will be based on SAF.

2.8.1 Adverse events (AEs)

A treatment-emergent AE is defined as any AE that develops after initiation of the study treatments or any event already present that worsens following exposure to the study treatment.

Treatment emergent AEs will be summarized. The number and percentage of subjects having AEs will be summarized by system organ class, preferred term, and treatment group. Unless otherwise specified, primary system organ will be sorted alphabetically and, within each primary system organ class, the preferred terms will be sorted in descending order of frequency in the LIK066 50 mg qd arm. If a patient reported more than one AE with the same preferred term, the AE will be counted only once. If a patient reported more than one AE within the same primary system organ class, the patient will be counted only once at the system organ class level. The number and percentage of subjects having AEs will be summarized by system organ class, preferred term, treatment group, and subgroups of interest (baseline glycemic status, age group and sex) as well.

The most frequent AEs ($\geq 5\%$ in LIK066 50mg qd arm group) will be presented by preferred term in descending order of frequency in the LIK066 50 mg qd arm.

AEs will also be presented by greatest severity. If a patient reported more than one AE with the same preferred term, the highest severity will be presented. All AEs will be summarized by highest severity, primary system organ class, preferred term, and treatment. If a patient reported more than one AE within the same primary system organ class, only one AE will be counted for that patient at the highest severity level in the total row for each primary system organ class. Missing severity will be assumed to be severe in the summary table.

AEs suspected to be related to study drug, serious AEs, fatal AEs, and AEs leading to study drug discontinuation, study drug interruption will be summarized by presenting number and

percentage of patients with an event by primary system organ class, preferred term, and treatment.

All AEs in the database will be listed. The listings will include those AEs reported during the run-in epoch, and AEs reported after study discontinuation for those who discontinue the study prior to Week 12.

Legal requirement for AE reporting

For the legal requirements of ClinicalTrials.gov, two required tables on treatment emergent AEs which are not SAEs with an incidence greater than 2% and on treatment emergent SAEs and SAEs suspected to be related to study treatment will be provided by system organ class, preferred term, and 5 randomized treatment arms on the SAF for overall study duration.

If for a same patient, several consecutive AEs (irrespective of study treatment causality, seriousness and severity) occurred with the same SOC and PT:

- a single occurrence will be counted if there is ≤ 1 day gap between the end date of the preceding AE and the start date of the consecutive AE
- more than one occurrence will be counted if there is > 1 day gap between the end date of the preceding AE and the start date of the consecutive AE

For occurrence, the presence of at least one SAE/SAE suspected to be related to study treatment/non SAE has to be checked in a block e.g., among AE's in a ≤ 1 day gap block, if at least one SAE is occurring, then one occurrence is calculated for that SAE.

The number of deaths resulting from SAEs suspected to be related to study treatment and SAEs irrespective of study treatment relationship will be provided by SOC and PT.

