9.8 Sample size calculation

The study planned to randomize approximately 130 subjects in total, allocated in the ratio of 3:2:2:3:3 to the following Epoch 3 treatment groups:

1. placebo
2. LIK066 2.5 mg qd
3. LIK066 10 mg qd
4. LIK066 25 mg qd
5. LIK066 50 mg qd

This randomization scheme implies that the Epoch 3 treatment for a specific subject is determined simultaneously at randomization visit. The randomization will be stratified by subjects' glycemic status: T2DM and dysglycemic (see [Section 3.1.2](#)).

Sample sizes are considered from two viewpoints. One is that this study should be statistically powered to identify the dose-response relationship regarding the effect of LIK066 on weight loss. The other is that this is the first study to enroll Japanese patients, and that the highest dose arms, 25 mg and 50 mg qd arms, and the placebo arm as a control, should include more patients to obtain sufficient information on safety and/or tolerability of LIK066 in Japanese patients. The detail of the first viewpoint will follow.

[Table 9-1](#) summarizes the average power and the lowest power across the candidate dose-response shapes in [Figure 9-1](#), under different scenarios with the assumptions on effect size of body weight loss (percent change from BL) for the dose of maximum effect, and the related standard deviations. In power evaluation, it was also assumed that dose-response is assessed with controlling the overall family-wise type I error at a one-sided significance level of 2.5%.

It was assumed that the effect of losses to follow-up is equivalent to effectively having 10% fewer subjects than randomized, even if the multiple imputation approach used to handle missing values should be able to recover some information for such subjects.

Table 9-1 Power for detecting a significant dose response signal*

Effect size for best dose	Standard deviation	Average power	Minimum power**
3.5%	3%	99.70%	99.52%
3.5%	3.5%	98.11%	97.28%
4.0%	3%	99.97%	99.94%
4.0%	3.5%	99.59%	99.35%

* Assumes 130 subjects in total with effective sample size of 117 subjects due to an effect of missing data equivalent to 10% fewer subjects. Calculations were performed using R Dose Finding package.

** Power for a significant dose-response contrast test across all scenarios mentioned in [Section 9.4.2](#). The quadratic model has the lowest power.

10 Ethical considerations

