20JUL2018	Prior to DBL	Change of cut-off value for AE frequencies	Summary of the most frequent AEs includes AEs whose frequencies are $\geq 5\%$ in 50mg qd arm.	2.8.1.1 Adverse events of special interest / grouping of AEs
20JUL2018	Prior to DBL	Clarification of diarrhea event for analysis of event periods	The number of days with "on-treatment" diarrhea is used for negative binomial regression analysis.	2.8.1.1 Adverse events of special interest / grouping of AEs
20JUL2018	Prior to DBL	Project-level update on analysis plan for hypoglycemic events	It is clarified to summarize "clinically significant" hypoglycemic events. Also it is updated how to use hypoglycemic events in AE summary.	2.8.1.1 Adverse events of special interest / grouping of AEs

Date	Time point	Reason for update	Outcome for update	Section and title impacted (Current)
20JUL2018	Prior to DBL	Project-level update on the AE of special interest	“Pre-amputation events” is additionally listed as AE of special interest.	2.8.1.1 Adverse events of special interest / grouping of AEs
20JUL2018	Prior to DBL	Clarification of cut-off values for shift tables	Cut-off values are specified for selected ECG parameters.	2.8.4.1 ECG and cardiac imaging data
[REDACTED]				
20JUL2018	Prior to DBL	Documentaton of the change in analysis plan from the protocol	It is clarified which analysis to be changed from the study protocol.	4 Change to protocol specified analysis
20JUL2018	Pror to DBL	To remove confusing information about handling of hypoglycemic event data	No impact	5.2 AEs coding/grading

Date	Time point	Reason for update	Outcome for update	Section and title impacted (Current)
20JUL2018	Prior to DBL	To add PD OTH01 to handle erroneous randomization	Any patient would be excluded from PPS if randomised under a CRC's erroneous operation at the site.	5.5 Rule of exclusion criteria of analysis sets
13SEP2018	Prior to DBL	To update the units for eGFR and FPG to SI units	The units in TFLs are updated.	2.3 Patient disposition, demographics and other baseline characteristics
13SEP2018	Prior to DBL	To clarify at which time point for BW to be summarized as baseline data	It becomes clear that screening BW is to be summarized.	2.3 Patient disposition, demographics and other baseline characteristics
13SEP2018	Prior to DBL	To add categorized summary on BL eGFR with Japanese coefficients	The plan for BL summary is updated.	2.3 Patient disposition, demographics and other baseline characteristics

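### The most-frequent-AE table selects its rows on the 50 mg arm alone, so within that one table it can omit terms common in other arms and overstates the 50 mg column

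*SAP*

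**What the plan says.** SAP 2.8.1 sets a 5% cut-off for the most-frequent-AE table, applies it to one arm and sorts by that arm: "in LIK066 50mg qd arm group) will be presented by preferred term in descending order of frequency" in that same arm. The SAP document history records this as a change of cut-off made on 20 July 2018, before database lock ("Summary of the most frequent AEs includes AEs whose frequencies are" at least 5% in the 50 mg arm), so it is current and intended text.

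Protocol 5.2 gives the planned arm sizes: "50 mg qd LIK066 (approx. 30 subjects"), "25 mg qd LIK066 (approx. 30 subjects"), "Placebo (approx. 30 subjects"), "2.5 mg qd LIK066 (approx. 20 subjects"), and about 20 at 10 mg. Protocol 9.8 explains that the 25 mg, 50 mg and placebo arms are larger because they "should include more patients to obtain sufficient information on safety and/or tolerability of LIK066 in Japanese patients".

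The same part of the SAP also plans:
- a table of all treatment-emergent events by system organ class, preferred term and treatment group, with no frequency cut-off, repeated by subgroup (2.8.1);
- tables by greatest severity and a listing of all events (2.8.1);
- a registry table of non-serious events above 2% by the five arms (2.8.1);
- special-interest event tables by treatment, with no frequency cut-off (2.8.1.1).

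**The concern.** A short table of frequent events is a natural place to compare tolerability across doses. Here the choice of rows depends on the observed count in one of the arms being compared, which has two effects.

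- **Omission.** A term with 0 or 1 case at 50 mg does not appear, however often it occurs at 25 mg, at a lower dose or on placebo.
- **Selection.** A term whose 50 mg count is high by chance gets a row, and one whose count is low by chance does not. The 50 mg column is therefore pushed upward, while the other columns, which play no part in the rule, are not.

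At stake is whether the arm comparison within this table is fair. Two of the three arms enlarged for safety information, 25 mg and placebo, have no say in what it shows.

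**Working it through.** **Inputs.** The cut-off is at least 5% in the 50 mg arm (SAP 2.8.1). The arms have about 30, 20, 20, 30 and 30 subjects for placebo, 2.5, 10, 25 and 50 mg (Protocol 5.2). True event rates are not in the documents, so I assume a true rate p and show a range. The plan states no operating figure for this table, so there is nothing of its own to reproduce beyond the cut-off.

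**Step 1: the cut-off as a count.** 5% of 30 is 1.5, so a term needs at least 2 subjects (2/30 = 6.7%). The same count applies for any arm of 21 to 40 subjects, so small departures from the planned size do not matter.

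**Step 2: probability that a term is shown.** Let X be the number of subjects with the event at 50 mg, X ~ Binomial(30, p). Then P(shown) = 1 − P(X=0) − P(X=1). At p = 5%: 1 − 0.2146 − 0.3389 = 0.446, so the term is omitted with probability 0.554.

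**Step 3: expected 50 mg rate in a displayed row.** E[X/30 | X ≥ 2] = (30p − P(X=1)) / (30 × P(X ≥ 2)). At p = 5%: (1.5 − 0.3389) / (30 × 0.4465) = 0.0867. The arms are independent, so the expected rate in every other arm stays at p.

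| True rate, all arms | Term omitted | Expected 50 mg rate if shown | Expected rate in other arms | Excess (points) |
|---|---|---|---|---|
| 2% | 88% | 7.4% | 2.0% | 5.4 |
| 3% | 77% | 7.8% | 3.0% | 4.8 |
| 5% | 55% | 8.7% | 5.0% | 3.7 |
| 10% | 18% | 11.7% | 10.0% | 1.7 |
| 15% | 5% | 15.6% | 15.0% | 0.6 |
| 20% | 1% | 20.2% | 20.0% | 0.2 |

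**Step 4: omission of a term frequent elsewhere.**
- With a true 5% in every arm, the chance that the row is missing while some other arm shows at least 10% observed is 36%.
- Suppose the true rate is 15% at 25 mg and 3% at 50 mg. The chance that 25 mg shows at least 10% (3 or more of 30) is 0.849. The chance that the row is missing is 0.773. Both happen with probability 0.849 × 0.773 = 0.66.

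**Step 5: a symmetric rule.** Admit a term if any arm has at least 5% and at least 2 subjects. With equal true rates, it is shown with probability 64% at p = 3%, 91% at 5% and 99.9% at 10%, against 23%, 45% and 82% under the current rule. Expected displayed rates are 3.6% (20-subject arms) to 3.8% (30-subject arms) at a true 3%, about 5.3% in every arm at a true 5%, and 10.0% in every arm at a true 10%.

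**The case against.** The strongest reply is that nothing is hidden from the report. The uncut table by arm and the listing contain every event. The risks predefined for this drug, including diarrhea, genital and urinary infections, hypoglycemia and volume depletion, have their own tables by arm with exposure-adjusted rates and relative risks. This stands, and it limits the point to one descriptive extract to which no test is attached.

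A second reply is that keying the extract to the top dose is a convention. It was fixed before database lock, matches the sort order of the main event table, and errs toward showing the highest dose in a worse light. That is fair as to intent. It does not make the columns of this table comparable, and the caution covers only 50 mg: a term seen mainly at 25 mg can still drop out.

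A third reply is that the size depends on assumed rates, and that at 3% to 5%, about one subject in 30, any frequency cut-off acts largely on chance. That also stands; for truly common events the effect almost vanishes. The ratio at a true 5% (8.7/5.0 = 1.73) describes a hypothetical event with no drug effect and is not an estimate that the trial will report.

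A reader might infer more: that this is the main tolerability display, that a 25 mg signal could be lost, or that dose choice would be biased against 50 mg. The documents do not support this. Neither gives the table that status. The purpose in Protocol 1.2 does include tolerability, but Protocol 9.4.2 bases target dose selection on the model-averaged weight response (averaging method updated in SAP 2.5.2), and the unselected comparison by arm is available in the uncut table.

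**Conclusion.** The point holds for the most-frequent-AE table and no further. Its row rule can leave out terms common in other arms, and it inflates the 50 mg column by about 5 points at a true rate of 2% to 3%, 3.7 points at 5% and 1.7 points at 10%; the inflation is negligible from about 15%. These figures assume about 30 subjects at 50 mg and the same true rate in every arm; the rates are assumptions. No safety data are lost and no inference depends on the table. It is a minor reporting matter, worth changing because the change is easy.

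**What to change.** In SAP 2.8.1, replace the row rule with: preferred terms reported in at least 5% and at least 2 subjects in any treatment arm, with all five arms shown. The 50 mg sort order can stay.

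The two-subject minimum is needed because one subject in a 20-subject arm is already 5%. Other filters do less well. A pooled rule of at least 5% of all subjects treats the arms alike, but shows a true-5% event with probability only 0.475, against 0.446 now. Adding a clause of at least 10% in any single arm triggers at 2/20 but 3/30, which moves a smaller bias to the low doses (5.0% there against 3.9% on placebo at a true 3%).

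The cost is one SAP sentence, one programming filter and some additional rows. No new data are needed.
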